3.2 Primary Study Endpoints

1. Frontostriatal reactivity to reward during the MID fMRI task
2. Response latency to reward versus non-reward during the MID fMRI task
3. Depressive symptoms

3.3 Exploratory Study Endpoints

1. Neural connectivity measured during resting-state fMRI

3.4 Primary Safety Endpoints

N/A

4 Subject Selection and Withdrawal

4.1 Inclusion Criteria

Participants will include healthy, unmedicated perimenopausal women ages 44-55 with ($n=20$) current major depression. Only participants capable of giving informed consent will be enrolled. Participants will be compensated upon completion of the study.

Inclusion Criteria.

1. **Perimenopause Status:** We will employ the Stages of Reproductive Aging Workshop (STRAW) criteria to confirm perimenopausal status. The stages are primarily based on characteristics of the menstrual cycle and secondarily on follicle stimulating hormone (FSH) levels. The anchor for the staging system is the last menstrual period (LMP). We will enroll women who have ≥ 2 skipped cycles with an interval of amenorrhea ≥ 60 days and had a LMP within the last year, consistent with the late menopause transition (stage -1). Women who meet these criteria will not require an FSH level*. Women who have taken oral contraceptives continuously for relief of perimenopausal symptoms and women who have had hysterectomies (with ovaries remaining intact) will be exempt from our LMP criteria, and their perimenopausal status will be determined by FSH level instead ($FSH \geq 14$)*.
2. **MDD Eligibility Criterion:** current diagnosis of MDD with an onset associated with menstrual cycle irregularity. Past mania, psychosis, suicide attempts, and alcohol or drug dependence, as determined by the Structure Clinical Interview for DSM-IV-TR for Axis I Disorders (SCID) are exclusionary. All other current comorbid psychiatric illnesses, as determined by the SCID, will be reviewed with our primary investigator (PI) to determine eligibility on a case-by-case basis.

4.2 Exclusion Criteria

Patients will not be permitted to enter this protocol if they have important clinical or laboratory abnormalities including any of the following:

1. current medication use (i.e., psychotropics, anti-hypertensives, statins, or hormonal preparations). Women will be allowed to enroll who take medications without known mood effects (e.g. stable thyroid hormone replacement and occasional (< 5 times/month) use of Ambien)*;
2. pregnant, breastfeeding or trying to conceive;
3. LMP more than 12 months prior to enrollment**;
4. history of undiagnosed vaginal bleeding;
5. undiagnosed enlargement of the ovaries;
6. polycystic ovary syndrome;
7. history of breast or ovarian cancer;
8. first degree relative with ovarian cancer;
9. first degree relative with premenopausal onset or bilateral breast cancer;
10. 2+ first degree relatives with breast cancer (regardless of onset);
11. 3+ relatives with postmenopausal breast cancer;
12. abnormal finding in a provider breast exam and/or mammogram***;
13. known carrier of BRCA1 or 2 mutation;
14. endometriosis;
15. blood clots in the legs or lungs;
16. porphyria;
17. diabetes mellitus;
18. malignant melanoma;

19. Hodgkin's disease;
20. recurrent migraine headaches that are preceded by aura;
21. gallbladder or pancreatic disease***;
22. heart or kidney disease***;
23. liver disease;
24. cerebrovascular disease (stroke);
25. current cigarette smoking;
26. current suicidal ideation, mania, psychosis, or alcohol/drug dependence;
27. past suicide attempts, mania, alcohol/drug dependence, or psychotic episodes;
28. chronic depression (i.e., episode(s) lasting 3+ years);
29. depressive episode(s) within 2 years of enrollment;
30. self-reported claustrophobia
31. Allergies to red or yellow dye.

*all reported prescription medications will be reviewed and cleared by a study physician prior to a participant's enrollment;

**women who have recently taken oral contraceptives continuously for relief of perimenopausal symptoms will be exempt from LMP criteria, and instead, the presence of menstrual irregularity prior to the use of oral contraceptives and elevated FSH will be used to determine their perimenopausal status;

***participants will be given the opportunity to describe these conditions in the online screening survey. Reported conditions that are acute in nature and/or benign will be reviewed by a study physician and exclusions will be decided case-by-case. All chronic conditions will be exclusionary.

4.3 Subject Recruitment and Screening

Methods of recruiting for this study include:

- Letters
- Flyers
- E-mail announcements
- Facebook advertisements
- Instagram advertisements
- Craigslist advertisements
- Newspaper and magazine advertisements

A number of women from our "Effects of Estradiol on Neural Reward System and Depression in the Perimenopause" (PEERS) study were ineligible on the basis of current depression. These women will be sent a letter as they may qualify for our study and have interest in participating. In addition, participants will be self-identified by responding to flyers in the community. A university wide email will also be used to recruit participants.

The letters described above will be used to recruit potential subjects. Recruitment materials (e.g., advertisements) will also be placed in university buildings and local businesses, and a university wide email will be used to recruit participants. Advertisements, including the letter, flyer, and email, will instruct participants to call our research lab to complete a phone screen or follow a link to our online eligibility survey. The phone screen and online eligibility survey include same questions (see attached).

Eligibility screening will include:

- An initial phone or online screening that includes questions about past medical and mental health history to assess potential participant's eligibility based on the criteria listed in sections 4.1 and 4.2.
- Participants will undergo a Clinical and Health Screening process to determine whether they are healthy enough to participate in this study. This screening will include past medical and mental health history and physical exam. During this evaluation, they will be asked questions about past and present psychiatric symptoms. They will also be asked to complete questionnaires about psychiatric symptoms. They may choose not to answer any or all of the questions for any reason.
- Participants will complete a safety questionnaire to determine whether they have any foreign iron or steel metal objects in their bodies, such as a pacemaker, shrapnel, metal plate, or metal debris. If they have any such objects in their bodies, they cannot participate in the MRI session.
- All participants will receive a pregnancy test. No pregnant women will be entered into the study, because the study drugs (Duavee) may be associated with fetal harm.

4.4 Early Withdrawal of Subjects

4.4.1 When and How to Withdraw Subjects

Participants with significant clinical or laboratory abnormalities will be discontinued from the study prior to estrogen administration.

Adverse mood symptoms will be monitored by administering the Hamilton Rating Scale for Depression (HRSD) at each study visit. If suicidal thoughts or severe mood symptoms are **observed at any period in the protocol, then the HRSD will be administered on consecutive days for three days. Anyone scoring > 20 on the HRSD or expressing concerns about their ability to continue in the study, will be considered to have severe mood symptoms and be discontinued from the protocol.** In the event of the occurrence of severe mood symptoms, the protocol will be terminated. Should this step prove to be unsuccessful, conventional medication will be prescribed as needed. Further, although we do not anticipate severe adverse reactions, we have arranged for inpatient hospital admission in the Psychiatry Department if symptoms are otherwise unmanageable.

Any patient experiencing clinically significant side effects such as nausea, hypertension, vomiting or extreme fluid retention from the medication will have the dose titrated to achieve relief of the symptoms. If adequate relief cannot be achieved in this manner, drug treatment will be discontinued.

The determination of when and how to withdrawal subjects will be overseen by the study's principal investigator, co-investigators, and research coordinators and will be reported to the UNC Biomedical IRB.

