1.4 Clinical Data to Date

We do not expect any adverse side effects associated with the hormonal manipulations outlined in this protocol for the following reasons: We will be administering estrogen paired with selective estrogen receptor modulators (SERMs) to a subset of women with perimenopausal women. SERMs are synthetic non-steroidal agents that have estrogen agonist and antagonist effects in different tissues, to block the negative effects of estrogen on non-target tissues, including the reproductive organs and cardiovascular system, while allowing estrogen to exert effects on target tissues like the brain, and thus decreasing risk for side effects.

Adverse Events Related to Combined Hormone Replacement and the Results of the Women's Health Initiative (WHI): The WHI study demonstrated that continuous administration of one form of estrogen (conjugated estrogens) in combination with one form of progesterone (medroxyprogesterone acetate) is associated with an increased risk of dementia, heart attacks, stroke, blood clots, and breast cancer. TSECs, the form of estrogen that we use in this study, is administered as a sole agent and, consequently, we do not expect that it will pose the increased risks observed with the chronic combination of the conjugated estrogens and medroxyprogesterone administered in the WHI study. Indeed, while the estrogen alone arm of the WHI trial was shown to be associated with an increased risk of stroke, no increased risk of either heart disease or breast cancer was observed^{55,56}. Estrogens may precipitate migraine headaches, and depression has also been reported to occur with the use of estrogens. In general, considering the dose and duration of treatment that we propose to use in this protocol, the risk of developing such side effects is negligible.

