4.4.2 Data Collection and Follow-up for Withdrawn Subjects

Participants who elect to discontinue the hormone protocol or are discontinued for safety reasons will be asked to continue to complete self-report ratings through the end of the proposed study period. However, fMRIs will not be done if participants discontinue the hormone protocol.

5 Study Drug

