7.2 Statistical Methods

Aim 1: Determine the extent to which TSEC reduces anhedonia and other depressive symptoms in PM-MDD. Anhedonia and other depressive symptoms will be assessed at baseline and following 3 weeks of TSEC administration. Null hypothesis (H0): TSEC has no salutary effect on depression. Alternative hypothesis (H1): TSEC reduces depression as evidenced by 1) a statistically significant decrease in average MASQ Anhedonia scale score following 3 weeks of treatment, and 2) a clinically significant increase of 1 SD in MASQ Anhedonia scale score. We will test this hypothesis using a paired t-test of MASQ Anhedonia scores at visit 1 (pre-treatment) and visit 6 (post-treatment).

Aim 2 (Exploratory): Quantify the effect of TSEC on the neural reward system in PM-MDD. We will use fMRI at baseline and following TSEC treatment in PM-MDD to probe frontostriatal reward circuitry. We also will compare the effects of TSEC and ERT in PM-MDD. Null hypothesis (H0): TSEC has no meaningful effect on activity of the neural reward circuit in response to rewards. Alternative hypothesis (H1): TSEC reduces increases neural responsiveness to reward in the frontostriatal reward circuitry as evidenced by increased activation of the caudate, putamen, and nucleus accumbens in PM-MDD in response to reward following TSEC administration (compared with baseline). We will test this hypothesis using a paired t-test to compare activity in 3 regions of interest (ROIs)—caudate, putamen, and nucleus accumbens—at the pretreatment and posttreatment scans.

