7.3 Subject Population(s) for Analysis

Given that we are interested in understanding the effect of TSECs on brain function, only data from protocol-compliant participants will be subjected to the study analysis.

8 Safety and Adverse Events

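### HRSD is collected to watch for adverse mood, but no planned analysis counts the women who worsened and no all-treated safety set is named

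*Combined protocol and SAP*

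**What the plan says.** Sections 4.4.1 and 8.5 and the individual stopping rules in Appendix A give HRSD a safety role: "Adverse mood symptoms will be monitored by administering the Hamilton Rating Scale for Depression (HRSD) at each study visit". Table 1 in Section 3.1 marks it at visits 1, 3, 4, 5 and 6, but not at visit 2. If suicidal thoughts or severe mood symptoms are seen, it is repeated on three consecutive days. "Anyone scoring > 20 on the HRSD or expressing concerns about their ability to continue in the study" is then discontinued.

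Section 1.4 notes that "depression has also been reported to occur with the use of estrogens", and the same paragraph calls such risks negligible at this dose and duration.

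The entry under "3.4 Primary Safety Endpoints" is N/A. Section 3.2 lists "3. Depressive symptoms" as a primary endpoint without naming an instrument. Section 7.2 specifies a paired t-test of MASQ Anhedonia (visit 1 against visit 6) and paired t-tests of three regions of interest. Section 7.3 states that "only data from protocol-compliant participants will be subjected to the study analysis". Under Section 4.4.2, women who stop "will be asked to continue to complete self-report ratings through the end of the proposed study period".

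**The concern.** Every participant is depressed at entry, and the protocol itself lists depression among the effects reported with estrogens. The scale chosen to detect worsening is given repeatedly, but the statistical plan does not use it.

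A mean improvement is compatible with a minority of women getting worse, and a paired t-test of means does not show how many. If women stopped for mood also fall outside the compliant set, the reported results would contain neither their scores nor a count of them. Section 1.1 describes the study as pilot data for a larger placebo-controlled trial. How many women deteriorated on treatment is something the planners of that trial would need to know.

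**Working it through.** **1. The plan's own figure.** Section 7.1 gives 80% power for an effect of 0.7 in 20 women. Alpha is not stated; I assume 0.05 two-sided.
- Normal approximation: n = ((1.960 + 0.842)/0.7)² = 16.02, so 17.
- Exact noncentral t: n = 19. At n = 20 the noncentrality is 0.7 × √20 = 3.13 and power is 84.4%.

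The sample size reproduces, slightly on the safe side, and is not in dispute.

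**2. Where could worsening appear?**

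| Place | Includes HRSD or a count of worsening? | Who is covered |
|---|---|---|
| 3.2, third primary endpoint | Instrument not named | Not stated |
| 3.4 | N/A | None |
| 7.2 | No; MASQ and regional means only | Set by 7.3 |
| 7.3 | No safety set | Compliant women; term undefined |
| 8.1, 8.2 | Worsening of a preexisting condition is an adverse event, but no HRSD criterion | All women |
| Appendix A, II.B | CTC grade and attribution per event | All events |
| Appendix A, III.B | Annual list of events and dropout reasons | All women; place in results not stated |

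**3. Does 7.3 remove women stopped for mood?** Compliance is discussed in Section 5.5 only as adherence to the drug regimen. A woman withdrawn under the protocol's own rule is not plainly non-compliant, but she has not completed the regimen. Exclusion is likely, not explicit. HRSD is also researcher-administered (Section 3.1), so the self-report follow-up in 4.4.2 does not extend it.

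**4. How many could worsen while the mean improves?** Assume individual change is normal and the standardised effect d applies to HRSD change. Section 7.1 does not tie 0.7 to HRSD, so this is an illustration.
- Fraction worse = Φ(−d).
- d = 0.7: Φ(−0.7) = 0.242; × 20 = 4.8 women.
- d = 1.15, the earlier estradiol study's figure, taken as mean change over SD of change: Φ(−1.15) = 0.125; × 20 = 2.5 women.

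Both count any score worse than baseline, noise included.

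**5. How should worsening be counted?** Suppose there is no effect, scores are exchangeable and ties are ignored.
- Any of visits 4, 5 or 6 above visit 3: the visit 3 score is the highest of four with probability 1/4, so 1 − 1/4 = 75% of women are flagged, or 15 of 20.
- Last on-drug score above visit 3, any rise: 1/2, or 10 of 20.

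A count of any rise would mostly report noise, so a margin is needed.

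**6. Precision.** If none of 20 women worsened, the exact two-sided 95% upper limit is 1 − 0.025^(1/20) = 16.8%. An interval should accompany the count.

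**The case against.** The strongest reply is that adverse-event reporting already covers this. Section 8.1 counts worsening symptoms, and specifically worsening of a preexisting condition, as adverse events. Section 8.2 records all of them with no compliance restriction. Appendix A grades and attributes each one and summarises them annually with dropout reasons, and Section 4.4.1 sends withdrawal decisions to the IRB. This stands. A reader might infer that deterioration would go wholly unreported; the documents do not support that. What remains is that no HRSD change is defined as an event, so classification is left to judgement in women already depressed, and nothing states that these summaries enter the trial results. The publication plan does not settle the matter either way.

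Three other tempting readings also fail:
- That any woman whose HRSD rises is discontinued. The rule uses an absolute score or voiced concern, so a woman rising from 10 to 18 is not stopped on score.
- That the protocol attributes depression to the drug. It says only that it has been reported with estrogens, and calls the risk negligible here.
- That 7.3 expressly excludes women stopped for mood. Its stated rationale is brain function, and it leaves compliance undefined.

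It is also fair to say that this is a 20-woman, three-week pilot and that HRSD doubles as a measure of symptom change. The scale of the study argues for a short table rather than against having one.

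**Conclusion.** The concern holds in a limited form. No safety endpoint, HRSD summary or all-treated analysis of mood worsening is specified. Worsening would surface only through adverse-event and dropout reporting, which has no HRSD criterion and no stated route into the results. A mean benefit in compliant women could thus be reported without any planned count of those who deteriorated.

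The possible size is illustrative only: about 24% (5 of 20) finishing worse at an effect of 0.7, and 12.5% (2 to 3 of 20) at 1.15. This assumes normal change and that the effect applies to HRSD, and it includes noise. The sample size and the Aim 1 test are not affected. This is a worthwhile, inexpensive improvement to the plan, not the correction of a wrong figure.

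**What to change.** In 3.4 and 7.3, state that safety is summarised in all women who took at least one tablet, whatever their compliance or discontinuation. In 7.2, report for that set:

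- (a) each woman's HRSD change from visit 3 to her last on-drug score, and her largest rise, using visits 4 to 6 and any unscheduled three-day assessments, which may be the only on-drug scores of a woman stopped before visit 4;
- (b) the number and percentage whose last on-drug HRSD exceeds visit 3 by a prespecified margin beyond measurement noise, with an exact 95% interval, and not any rise at any visit. The documents give no measurement-error figure, so the sponsor must set and justify the margin before looking at the data;
- (c) the number discontinued for mood;
- (d) adverse events by CTC grade and attribution.

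State that, without a control, the counts are descriptive and not attributable to the drug. Reconcile the statement in 4.4.1 that HRSD is given at every visit with Table 1, which omits visit 2.

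The cost is a few sentences and one short table from data already planned, with no new visits or measurements. The downside is that the table may look less favourable than the mean. No change to any dose, threshold or withdrawal rule is proposed.

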3.1 General Design

Overview. This is an observational, single-center study using tissue-selective estrogen complex (TSEC) to examine the role of frontostriatal hypoactivity in the pathophysiology of perimenopausal MDD. This study will include 6 study visits that will take place over the course of approximately 6 weeks. Out of those 6 visits, 2 of them will require subjects to come to UNC's campus for their MRI visits at BRIC, while the rest of the appointments will be done virtually through HIPAA compliant Zoom, Webex, or phone when zoom is not available. Five visits will require brief in-person contact for phlebotomy, these very brief points of contact will be performed outside the subject's home when possible (i.e. backyard, back porch, or screened porch). In the context of COVID-19, all participants and staff will complete the appropriate screening as recommended by UNC and BRIC policy prior to any in-person contact. During in person visits participants and the study team will be required to wear masks at all times and maintain 6 feet distance when possible to minimize the possibility of COVID-19 transmission. Perimenopausal MDD women will receive Duavee, a TSEC, for 3 weeks. FMRI sessions will occur at baseline and at the end of the third week of medication administration. The procedures that will take place are outlined in **Table 1** and detailed below.

Table 1. Study Procedures and Timeline

Study Visits	1	2	3	4	5	6
Maximum duration of in-person visit (hours)		1	2	0.15	0.15	2
Consent	X					
OBGYN Exam		X				
fMRI			X			X
PRT			X			X
Venipuncture		X	X	X	X	X
SCID	X					
SNAP	X		X	X	X	X
HAM-D	X		X	X	X	X
IDAS	X		X	X	X	X
GCS	X		X	X	X	X
PSQI			X			X
HHQ						X
THQ						X
Duavee Rx Provided			X	X	X	
Payment	\$100	\$30	\$150	\$35	\$35	\$150

Participants. Participants will include healthy, unmedicated perimenopausal women ages 44-55 with (n=20) current major depression.

Hormone Administration.

Prior to beginning medication, women will have a basic lab panel and serum pregnancy test, pelvic exam, breast exam, and PAP smear. Participants who can provide record of a pelvic exam and breast exam within the past year and normal pap results within the past three years will be permitted to decline the GYN exam. Women will be seen in the clinic each week during medication administration to assess blood levels of estradiol and mood symptoms.

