Optional Home Visits: In an effort to increase recruitment and retention, the study team will offer home visits for Study Visits 1, 4, 5, as well as Baseline Labs.

Clinical Assessments

The Structured Clinical Interview for DSM-IV-TR Axis-I Disorders (SCID)⁵⁸ and the Schedule for The SCID1 will be administered at baseline to determine study eligibility. The following standard measures will be administered at baseline, both fMRI sessions, and weekly clinic visits:

- The Positive and Negative Affect Schedule⁵⁹ is a 20-item questionnaire that measures both positive affect (PA) and negative affect (NA) and is sensitive to subtle changes in affect over time.
- The Hamilton Rating Scale for Depression (HRSD)⁶⁰ is a 21-item researcher-rated standardized scale that assesses depressive symptoms and is widely used as a measure of symptom change over time.
- The Inventory of Depression and Anxiety Symptoms (IDAS)⁶¹ is a 64-item self-report questionnaire that comprehensively assesses anxiety and depression symptoms on 10 subscales. The IDAS has excellent psychometric properties and has been validated for assessing reproductive mood disorders.
- The Mood and Anxiety Symptom Questionnaire – Anhedonic Depression Subscale (MASQ-AD)⁶² is a 22-item scale that assesses anhedonia (i.e., loss of interest and low positive affect). MASQ-AD scores have been associated with blunted striatal response to reward in previous studies of patients with depression⁶³.
- The Greene Climacteric Scale (GCS)⁶⁴ is a 21-item scale that is the gold-standard measure of four domains of climacteric symptoms: vasomotor, somatic, anxiety, and depression.
- The Pittsburgh Sleep Quality Index (PSQI)⁶⁵ is a 9-item questionnaire that measures the quality and sleep patterns in older adults. *This measure will only be administered at the two fMRI sessions.
- The Hormone History Questionnaire is a 19-item inventory that assesses women's mental and physical health and was created for the purpose of this study.
- The Trauma History Questionnaire¹⁴ is a 24-item measure that examines participant's experiences with potentially serious or traumatic life events.

While the SCID and HAM-D are researcher administered, the other measures will be collected through self-report questionnaires using Qualtrics or paper and pencil questionnaires.

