1. **Perimenopause Status:** We will employ the Stages of Reproductive Aging Workshop (STRAW) criteria to confirm perimenopausal status. The stages are primarily based on the characteristics of the menstrual cycle and secondarily on follicle stimulating hormone (FSH) levels. The anchor for the staging system is the final menstrual period (FMP). We will enroll women who have ≥ 2 skipped cycles and an interval of amenorrhea ≥ 60 days, consistent with the late menopause transition (stage -1). Women who meet these criteria will not require an FSH level. Women who have taken oral contraceptives continuously for relief of perimenopausal symptoms and women who have had hysterectomies (with ovaries remaining intact) will be exempt from our LMP criteria, and their perimenopausal status will be determined by FSH level instead ($FSH \geq 14$). Because extremes of body weight ($BMI < 18$ or > 35 kg/m 2) or a history of chronic menstrual cycle irregularity can contribute to inaccurate reproductive staging, these will serve as additional exclusion criteria;
2. **MDD Group Eligibility Criterion:** current diagnosis of MDD with an onset associated with menstrual cycle irregularity, and no history of psychiatric illness during the 2 years before the onset of the current depressive episode as determined by the Structured Clinical Interview for DSM-IV-TR for Axis I Disorders (SCID)

Exclusion Criteria. Patients will not be permitted to enter this protocol if they have important clinical or laboratory abnormalities including any of the following:

1. current medication use (i.e., psychotropics, anti-hypertensives, statins, hormonal preparations, or frequent use of anti-inflammatory agents (> 10 times/month)). Women will be allowed to enroll who take medications without known mood effects

(e.g. stable thyroid hormone replacement and occasional (< 5 times/month) use of Ambien)*;

2. pregnant, breastfeeding or trying to conceive;
3. LMP more than 12 months prior to enrollment**;
4. history of undiagnosed vaginal bleeding;
5. undiagnosed enlargement of the ovaries;
6. polycystic ovary syndrome;
7. history of breast or ovarian cancer;
8. first degree relative with ovarian cancer;
9. first degree relative with premenopausal onset or bilateral breast cancer;
10. 2+ first degree relatives with breast cancer (regardless of onset);
11. 3+ relatives with postmenopausal breast cancer;
12. abnormal finding in a provider breast exam and/or mammogram***;

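### The HRSD > 20 stopping rule is absolute and applies at any time, but entry sets no HRSD ceiling: eligible women can meet it before dosing, and women doing badly on drug can drop out of the pre-post comparison

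*Combined protocol and SAP*

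**What the plan says.** **Stopping rule.** Sections 4.4.1 and 8.5 and Appendix A III.C carry the same rule. Once severe mood symptoms or suicidal thoughts have been "observed at any period in the protocol, then the HRSD will be administered on consecutive days for three days". Then: "Anyone scoring > 20 on the HRSD or expressing concerns about their ability to continue in the study" counts as having severe mood symptoms and is discontinued. After that, if needed, "conventional medication will be prescribed as needed". None of the three places refers to the woman's own baseline score or starts the rule at first dose.

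**Entry.** Section 4.1 requires a "current diagnosis of MDD with an onset associated with menstrual cycle irregularity". Appendix A asks for a "current diagnosis of MDD with an onset associated with menstrual cycle irregularity, and no history of psychiatric illness during the 2 years before" the current episode. The nearest thing to a severity limit is the exclusion of "current suicidal ideation, mania, psychosis, or alcohol/drug dependence" (4.2, repeated in Appendix A). No list gives an HRSD maximum.

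**Timing.** Section 3.1: "The following standard measures will be administered at baseline, both fMRI sessions, and weekly clinic visits". Table 1 marks the HAM-D at visits 1, 3, 4, 5 and 6. Sections 5.7 and 6 supply the tablets at visit 3. On imaging, 3.1 says: "FMRI sessions will occur at baseline and at the end of the third week of medication administration"; Table 1 puts these scans at visits 3 and 6.

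**After a stop.** Section 4.4.2 rules out further scans once the hormone protocol is discontinued, but asks the woman to keep completing self-report ratings. Section 7.3 analyses protocol-compliant participants only and does not define the term. Section 7.2 tests Aim 1 with a paired t-test of MASQ anhedonia, visit 1 against visit 6.

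**The concern.** The entry criteria admit a woman whom the stopping rule then removes on a score she already had. That conflict should be settled before enrolment, because it decides who the study population is and whether a pre-dose stop counts toward the 20.

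The on-drug consequence matters more for inference. The rule acts on a depression score measured after dosing, and the study asks whether depression falls after dosing. Women doing badly are the ones stopped. With no placebo group (1.1), no comparator would show that loss. The protocol also calls the study pilot data for a larger placebo-controlled trial, so a favourable distortion would carry forward.

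**Working it through.** **1. Can an eligible woman meet the rule before dosing?**

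| Visit | HRSD | Drug status | Effect of a score > 20 |
|---|---|---|---|
| 1 | yes | before dose | rule can be met |
| 3 | yes | first supply, baseline scan | rule can be met |
| 4, 5 | yes | on drug | stop, no second scan |
| 6 | yes | second scan and final rating | endpoint visit itself |

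The rule covers any period, HRSD is rated twice by the visit at which drug is first supplied, and no criterion caps the score. So yes. Excluding current suicidal ideation removes one trigger at entry but does not limit the score.

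**2. Whom does it remove on drug?** Severe mood symptoms is both the trigger for the three-day repeat and the label given to a score above 20, so the text supports two readings.

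- *Every score counts.* A woman above 20 at visit 1 or 3 leaves before dosing. Anyone above 20 at visit 4 or 5 was therefore at or below 20 at visit 3 and has crossed the line. A rise from 20 to 21 is enough.
- *The cut-off applies only once the repeat is triggered.* A woman above 20 at visit 3 may be dosed if nobody invokes the trigger, and then stopped at visit 4 or 5 while still above 20. The text does not say how many of the three repeat scores must exceed 20.

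Either way, removal depends on a high depression score after dosing.

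**3. What is lost?** The second scan is lost for every woman stopped on drug (4.4.2), so she leaves the Aim 2 paired test. For Aim 1 the answer depends on 7.3. A woman who took her tablets until she was stopped meets the adherence standard in 5.5, yet she did not complete the protocol. The text does not say whether she is compliant.

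**4. Direction, under assumed inputs.** The documents give no HRSD mean, SD or correlation. Assume normal scores, SD 5, pre-post correlation r = 0.6, no drug effect, and one post-dose rating with removal above 20 (cut at 20.5). With z = (20.5 − mean)/5, the apparent mean change among retained women is −(1 − r) × SD × φ(z)/Φ(z). At mean 18, z = 0.5, so −0.4 × 5 × 0.3521/0.6915 = −1.02 points. At means 14, 16 and 20 it is −0.38, −0.65 and −1.47.

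Those figures have no entry limit. If entry is also cut at 20.5, symmetry gives all dosed women a change of the same size upward (+1.02 at mean 18), and a simulation put retained women close to zero (−0.01). So dropping stopped women moves the estimate toward benefit on both readings, but on the first it offsets an upward drift and does not create an apparent benefit from nothing. This concerns HRSD at the rating where the rule acts. It is not an estimate for MASQ at visit 6.

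**5. Power.** Section 7.1 claims 80% power at d = 0.7 with 20 women. Assume two-sided alpha 0.05 (not stated there). The paired t-test has df = n − 1 and noncentrality d√n. For n = 20: 0.7 × √20 = 3.130, critical t = 2.093, power 84.4%. The smallest n reaching 80% is 19, so the plan's figure holds.

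| n analysed | d = 0.7 | d = 1.15 |
|---|---|---|
| 20 | 84.4% | 99.8% |
| 19 | 82.3% | |
| 18 | 79.9% | |
| 16 | 74.5% | 99.0% |
| 9 | | 85.5% |

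Pre-dose stops reduce n only if they count toward the 20 and are not replaced, which the text does not say.

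**The case against.** An absolute ceiling is a defensible safety choice. These women have current major depression, take no antidepressant, and receive an agent whose effect on depression the protocol calls untested. Stopping a severely depressed woman and offering standard treatment protects her whether or not she has worsened. **This stands**, and it is why a worsening-from-baseline rule is not proposed as a replacement: it could keep a woman with a stable, very high score on an unproven drug.

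A reader might infer that the rule will routinely stop women who have not worsened. **Not supported.** If every score counts, women above 20 leave before dosing and anyone stopped at visit 4 or 5 has risen past 20. Only the triggered-repeat reading allows a stop without worsening.

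A reader might also infer that staff have no instruction for a woman above 20 before dosing. **Not supported if every score counts**, since she is then discontinued. What is missing is the matching entry criterion, a statement of which score governs, and whether she is replaced.

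Sections 3.1 and 6 speak of a woman who *develops* severe symptoms, which hints at worsening. They give no threshold and do not amend the rule. Investigator oversight of withdrawals (4.4.1) supplies no threshold either.

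Finally, the only certain loss is the second scan, and Aim 2 is labelled exploratory. That is fair, though 3.2 lists frontostriatal reactivity first among the primary endpoints.

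**Conclusion.** The point holds as an inconsistency between entry and stopping rules, plus outcome-dependent loss on drug. The pre-dose conflict follows directly from the text. Loss of the second scan is certain for any woman stopped on drug; loss from Aim 1 is possible and turns on an undefined term in 7.3.

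Neither the share of women affected nor the size of any bias can be computed, because no entry HRSD distribution is given. A reader might infer that the sample size is compromised. The figures do not support that: at d = 0.7 power stays close to 80% with 18 women, and at the anticipated d = 1.15 it remains high even with 9. Selective loss is the main concern.

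This should be fixed, with medium confidence. The power figures rest on two-sided alpha 0.05, and the direction argument on the inputs assumed above.

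**What to change.** **1. Align entry with the rule.** Keep the absolute ceiling. Add HRSD <= 20 before dosing to the criteria in 4.1/4.2 and Appendix A, and treat women above it at visit 1 or 3 as screen failures who are replaced. In 4.4.1, 8.5 and III.C, state whether a single score or the repeat scores govern and, if the repeats, how many must exceed 20. Make suicidality a separate trigger that needs no HRSD score. Bring the *develops* wording in 3.1 and 6 into line. *Cost:* wording only, but the study population is then explicitly limited to HRSD <= 20, and results speak only for it.

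**2. Define the Aim 1 set.** In 7.3, analyse all women who took at least one dose and have a visit 6 MASQ score, including those stopped under the rule, using the ratings 4.4.2 already requests. Keep a defined protocol-compliant set as one sensitivity analysis, and use the last score before rescue treatment as another. Report the number stopped before and after dosing. *Cost:* no new visits or instruments. Early stopping may dilute the effect, rescue medication may contaminate late scores, and some ratings will be missing because stopped women are only asked to continue. This assumes the MASQ is collected as 3.1 and 6 list it; neither schedule table gives it a row.
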